5.4. General Concomitant Medication and Supportive Care Guidelines

The use of any natural/herbal products or other “folk remedies” are not allowed on study. All medications must be recorded in the case report form and be reviewed by the treating physician at each visit.

Cediranib demonstrated minimal inhibitor effects on the activity of CYP3A4 (testosterone and midazolam) in vitro, although the IC50 was far in excess of the clinically relevant

concentrations. Based on in vitro and clinical exposure data, olaparib is considered unlikely to cause clinically significant drug interactions through inhibition or induction of cytochrome P450 enzyme activity. However, in vitro data have also shown that the principal enzyme responsible for the formation of the 3 main metabolites of olaparib is CYP3A4. Given this data, potent inhibitors or inducers of CYP3A4 (as outlined in Appendix D) must not be used during this study for patients receiving olaparib. Dihydropyridine calcium-channel blockers are allowed for management of hypertension.

Patient should receive general concomitant and supportive care medications based on best medical practice. Neupogen and other bone marrow-supportive agents, including erythropoiesis-stimulating agents, are not allowed during treatment.

5.5. Duration of Therapy

Duration of therapy will depend on individual response, evidence of disease progression and tolerance. In the absence of treatment delays due to adverse events, treatment may continue indefinitely or until one of the following criteria applies:

- Disease progression,
- Intercurrent illness that prevents further administration of treatment,
- Unacceptable adverse event(s),
- Participant decides to withdraw from the study, or
- General or specific changes in the participant's condition render the participant unacceptable for further treatment in the opinion of the treating investigator.

5.6. Duration of Follow Up

Participants will be followed for 3 years after removal from study treatment or until death, whichever occurs first. Participants removed from study treatment for unacceptable adverse events will be followed until resolution or stabilization of the adverse event. Participants' vital status will be followed every 6 months following removal from the study treatment. Date and cause of death should be provided for participants who become deceased within the 3 year interval following removal from the study treatment.

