- j: ECG done prior to Cycle 1 and 2, and then prior to every cycle if clinically indicated. The pre-study ECG may be used as the Cycle 1 ECG if performed within 7 days of Cycle 1 Day 1.
- k: MUGA or echocardiogram should be done at baseline and every 4 cycles for those patients at increased risk for compromised LVEF. Increased risk patients have had one or more of the following: (1) prior treatment with anthracyclines, (2) prior treatment with trastuzumab, (3) NY Heart Association classification of II, (4) prior central thoracic RT, (5) history of myocardial infarction within the 12 months prior.
- l: beta-HCG for women of childbearing potential.
- m: Tumor measurements by CT scans or MRI will be performed within the 4 weeks prior to starting cediranib/olaparib and will be performed after every 8 weeks (+/- 1 week) of treatment. If a partial or complete response is noted, a confirmatory CT scan or MRI should be performed. The next planned restaging CT scan or MRI may be used as the confirmatory scan. For patients in the Phase 2 portion of the trial, the frequency of restaging studies will decrease to once every 12 weeks (+/- 1 week) after the 20th cycle of treatment.
- n: The Family Risk Assessment questionnaire (Appendix I) should be completed by the patient and returned to the study staff by Cycle 2.
- o: For patients opting to participate in translational studies at the NCI. Study schedules will be as per Section 5.1.4.
- p: Off-treatment assessments should be performed within 30 days of stopping study treatment.
- q: For patients in the Phase 2 portion of the trial who have been on trial for greater than 4 years without evidence of disease progression, the treating investigator may choose to decrease the frequency of re-staging CT scans to once every 4 cycles.
- r: For patients in the Phase 2 portion of the trial who have been on trial for greater than 4 years without evidence of disease progression, the treating investigator may choose to decrease the frequency of visits to once every 2 cycles. These patients should have CBC with differential, serum chemistry, and urine protein assessment (UPC or urinalysis) performed and con-meds, adverse events, and blood pressure diary should be reviewed in-person or by telephone with the study team, but all other assessments may be omitted.

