The expected PFS to a platinum-based regimen in this setting is approximately 6 months (Markman *et al.*, 1991). The PFS observed with cediranib alone in this patient population was 5.2 months (Matulonis *et al.*, 2009). In the Phase II study of olaparib in BRCA mutation carriers, the estimated PFS ranged from approximately 2.5 months to 5.5 months between the 100mg BID and 400mg BID cohorts (Audeh *et al.*, 2010). In BRCA wild-type patients, the estimated response rate was 23.9% (Gelmon *et al.*, 2010), which is comparable to the 20% response rate observed with single-agent cediranib (Matulonis *et al.*, 2008). Given this similar activity and the observed data in the Audeh *et al.* Phase II trial, we therefore project a PFS in a control arm of olaparib alone to be similar to that of platinum-based regimens at 6 months. An increase in progression-free survival to 10.5 months (from the projected 6 months) would be considered of clinical interest. In the Phase II portion of the study, for a power of 86% to reject H_0 : Median PFS in both arms = 6 months in favor of H_1 : Median PFS of the group with olaparib combination > 10.5 months with an alpha of 0.10, 71 events (i.e., disease progressions) out of a total of 82 evaluable patients will be required to detect a hazard ratio of 0.5716 (experimental over control). We will therefore perform the final PFS analysis when the 71st evaluable patient experiences cancer progression. It is anticipated that 10% of subjects will not be evaluable, and thus the total number of subjects with platinum-sensitive disease to be enrolled in the Phase II portion of the study is 90. Progression-free survival will be evaluated by Kaplan-Meier analysis and Log-Rank test for between group comparison, and median survival times reported. To minimize the likelihood of exposing study patients to an inactive regimen, an interim assessment of the hazard ratio for disease progression (experimental over control) will be performed when the 36th patient experiences cancer progression. If the estimated hazard ratio at that time is 1 or greater, accrual to the study will be halted for futility.

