Response rates with olaparib in patients with recurrent ovarian cancer have been reported at approximately 20% (Gelmon *et al.*, 2010). Second-line platinum results in a response rate of ~30% in patients who have had a treatment-free interval between 6 and 24 months. With an enrollment of 41 patients in each arm, there will be an 80% power to detect a difference in tumor response and clinical benefit rates as small as 29.5% with an alpha of 0.05. H_0 : single-agent olaparib response rate = cediranib and olaparib response rate = 20%. H_1 : cediranib and olaparib > 49.5%. The response rates will be compared by an exact test and 95% confidence intervals will also be reported.

The secondary endpoint of overall survival will also be evaluated by Kaplan-Meier analysis and Log-Rank test for between-group comparison, and median survival time will be reported.

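### Survival follow-up ends 3 years after each patient stops treatment, so Kaplan-Meier overall survival beyond month 36 can be too high if time on treatment predicts later survival (minor)

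*Combined protocol and SAP*

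**What the plan says.** Section 5.6 sets the length of follow-up from the end of treatment: "Participants will be followed for 3 years after removal from study treatment or until death, whichever occurs first". It adds that "Participants' vital status will be followed every 6 months following removal from the study treatment", and limits the collection of deaths to the same window: "Date and cause of death should be provided for participants who become deceased within the 3 year interval following removal from the study treatment".

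Section 5.5 puts no limit on treatment: "treatment may continue indefinitely or until one of the following criteria applies". The criteria it lists include progression, intercurrent illness, unacceptable adverse events, withdrawal and investigator judgment. The Phase II calendar (Section 9.2) provides for patients "who have been on trial for greater than 4 years without evidence of disease progression".

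For the analysis, Section 14.2 says "The secondary endpoint of overall survival will also be evaluated by Kaplan-Meier analysis and Log-Rank test for between-group comparison". It gives no OS data cut-off, censoring rule, event count, analysis date or sensitivity analysis. No other section extends survival follow-up or sets a common cut-off.

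**The concern.** Kaplan-Meier and log-rank methods assume that, within an arm, patients censored at a given time have the same outlook as those still under observation. Under Section 5.6 a survivor leaves observation at time on treatment plus 36 months. A patient who stops in month 2 and lives on leaves at month 38; one treated for 4 years can be followed to year 7. Past month 36, the patients still observed are increasingly those who were treated longest. If they also live longer after stopping, they no longer represent those who left, and the late part of the curve is too high. Deaths outside the window are not requested and may be hard to recover afterwards.

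What is at stake is the late part of the Phase II OS curves. The primary PFS analysis is not touched.

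**Working it through.** **1. The plan's own figure.** Inputs from Section 14.2: 71 events, hazard ratio 0.5716, alpha 0.10, and median PFS from "we therefore project a PFS in a control arm of olaparib alone to be similar to that of platinum-based regimens at 6 months" and "An increase in progression-free survival to 10.5 months (from the projected 6 months) would be considered of clinical interest". The medians give 6/10.5 = 0.571. One-sided power is Φ(√(71 × 0.25) × |ln 0.5716| − 1.2816) = Φ(2.356 − 1.282) = Φ(1.075) = 85.9%, which matches the stated 86%. There is no OS figure to reproduce.

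**2. Follow-up limit under the plan's medians.** Take time on treatment as exponential, ending at progression. The limit is then T + 36 months from treatment start.

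| | Median | 10th to 90th percentile |
|---|---|---|
| Control (median T = 6) | 42.0 months | 36.9 to 55.9 |
| Combination (median T = 10.5) | 46.5 months | 37.6 to 70.9 |

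Stopping for other reasons would shorten T.

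**3. When the rule starts to act.** T cannot be below 0, so no treated patient is censored by it before month 36. The 71st PFS event is expected when N × the average over arms of {1 − [exp(−λ(t−18)) − exp(−λt)]/(18λ)} = 71, with λ = ln 2/6 and ln 2/10.5 and 18 months of accrual. This gives t = 28.4 months if all 90 patients contribute and 34.1 if 82 do. Both precede month 36.

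**4. Who can be observed at month 60.** Only patients with T of at least 24 months: 2^(−24/6) = 6.25% of control (2.8 of 45) and 2^(−24/10.5) = 20.5% of combination (9.2 of 45), before allowing for deaths.

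**5. Size of the late error.** Simulation: OS = T + survival after stopping, with survival after stopping exponential. Its median and its correlation with T (Gaussian copula) are assumptions, because the documents give neither. At 60 months with correlation 0.5, true survival against Kaplan-Meier under the rule (differences taken before rounding):

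| Assumed median after stopping | Control | Combination | At risk of 45 (control / combination) |
|---|---|---|---|
| 12 months | 8.2% → 10.1% (+1.9) | 14.1% → 15.4% (+1.4) | 1.6 / 4.9 |
| 18 months | 16.6% → 20.5% (+3.9) | 22.5% → 25.4% (+2.8) | 2.0 / 6.2 |
| 24 months | 24.5% → 30.0% (+5.5) | 30.3% → 34.2% (+3.9) | 2.3 / 7.1 |
| 30 months | 31.5% → 37.9% (+6.4) | 36.9% → 41.6% (+4.7) | 2.4 / 7.6 |

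At 36 months the error is zero in every row. With correlation 0, the error at 60 months is 0.3 to 0.4 points in control and 1.0 to 1.3 in combination. It is not exactly zero because, in this model, patients still on treatment are not yet at risk of death.

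**6. Deaths not recorded.** With an assumed calendar cut at 84 months, 18-month accrual and medians of 18 to 30 months, about 13 to 27% of the deaths before the cut fall outside the 3-year window.

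**7. Effect on the comparison** (200,000 patients per arm, assumed median 24 months). With correlation 0.5, the hazard ratio is 0.854 under the rule. It is 0.833 when the same censoring times are permuted within arm, so that they carry no information. The difference, 0.021, is what dependent censoring contributes, and it goes against the combination. With an assumed 60 deaths, SE(log HR) ≈ √(4/60) = 0.26, and ln(0.854/0.833) = 0.025, about one-tenth of a standard error.

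**8. Type I error.** With equal OS in both arms (medians 30, 36, 48 months), treatment medians 6 and 10.5, correlation 0, 0.4 or 0.7, 45 per arm and 4,000 runs each, two-sided 5% log-rank rejection was 4.4 to 5.6% under the rule and 5.0 to 6.0% without it. The simulation error is √(0.05 × 0.95/4000) = 0.3 points.

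**The case against.** The strongest case for leaving the plan alone is that a fixed post-treatment survival window is an ordinary resource choice in a 90-patient phase II trial. OS has no power statement, error rate or decision attached. The affected region holds only a handful of patients, and median OS is affected only if it exceeds 36 months. The plan also writes no OS censoring rule: censoring at removal plus 3 years is inferred from the fact that later deaths are not requested. All of this stands, and it sets the severity.

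Three stronger readings are tempting, and the documents do not support them.

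- A reader might infer that the rule tilts the OS hazard ratio toward the combination. With correlation 0 and median 24 months, the ratio does move from 0.818 at an 84-month calendar cut to 0.781 under the rule. But permuting the censoring times within arm gives 0.783, and a common calendar cut at 54 months gives 0.779. The shift reflects a shorter window under non-proportional hazards, not dependent censoring.
- A reader might infer that unequal follow-up between arms is itself a bias. Kaplan-Meier and log-rank remain valid when censoring differs by arm, provided it is independent of outcome within each arm.
- A reader might infer that late OS is biased whatever happens. The direction and size rest on the link between time on treatment and later survival, on which the documents are silent.

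What the objection does not remove is that observation time depends on a post-randomization outcome that is plausibly prognostic, and that nothing in Section 14.2 deals with it.

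**Conclusion.** The point holds in conditional form and is minor. Maximum OS follow-up is time on treatment plus 36 months, with the clock starting at removal for any reason, not only progression. OS estimates up to month 36, and any OS analysis near the final PFS analysis, are unaffected.

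Beyond month 36, a positive relation between time on treatment and later survival makes Kaplan-Meier OS too high in both arms: roughly 1 to 7 points at 60 months for correlation 0.5 and post-treatment medians of 12 to 30 months, and about 1.5 points or less with no correlation. The plan supplies the treatment-time medians; the post-treatment medians, the correlation and the 84-month cut are assumptions. The hazard-ratio effect attributable to dependent censoring is about 0.02, and no type I inflation was seen in the scenarios run. PFS power, events and sample size do not change.

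**What to change.** In Section 5.6, continue the existing 6-monthly vital-status contact for all Phase II patients until death or one common calendar cut-off, and request date and cause of death over the same period. In Section 14.2, name that cut-off for the OS analysis. This removes this source of bias by construction. The cost is a few extra contacts for patients alive more than 3 years after stopping treatment.

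If contacts cannot be extended, report Kaplan-Meier OS beyond 36 months from treatment start only with a caveat on this censoring, or with a censoring-weighted sensitivity analysis. Weighting is the weaker remedy. Given time on treatment, censoring at T + 36 is certain, so at month 60 there is no patient who stopped before month 24 left to weight up. The weights would have to rest on other covariates or on a model, which is a reason to prefer collecting the deaths.

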5.7. Criteria for Removal from Study Treatment

Participants will be removed from study treatment when any of the criteria listed in Section 5.5 applies. The reason for study treatment removal and the date the participant was removed must be documented in the study-specific case report form (CRF). Alternative care options will be discussed with the participant.

In the event of unusual or life-threatening complications, participating investigators must immediately notify the Principal Investigator, [name] at [contact] (pager).

6. EXPECTED TOXICITIES AND DOSING DELAYS/DOSE MODIFICATIONS

Dose delays and modifications will be made using the following recommendations. Toxicity assessments will be done using NCI Common Terminology Criteria for Adverse Events (CTCAE v5.0). CTCAE v 5.0 is identified and located on the CTEP website at (http://ctep.cancer.gov/protocolDevelopment/electronic_applications/ctc.htm).

If possible, symptoms should be managed symptomatically. In the case of toxicity, appropriate medical treatment should be used (including anti-emetics, anti-diarrheals, etc.).

All adverse events experienced by participants will be collected from the time of the first dose of study treatment, through the study and until the final study visit. Participants continuing to experience toxicity at the off study visit may be contacted for additional assessments until the toxicity has resolved or is deemed irreversible.

6.1. Anticipated Toxicities

A list of the adverse events and potential risks associated with the agents administered in this study appear below and will determine whether dose delays and modifications will be made or whether the event requires expedited reporting **in addition** to routine reporting.

6.1.1. CAEPRs for CTEP-Supplied Investigational Agents

The Comprehensive Adverse Event and Potential Risks list (CAEPR) provides a single, complete list of reported and/or potential adverse events (AE) associated with an agent using a uniform presentation of events by body system.

In addition to the comprehensive list, a subset, the Agent Specific Adverse Event List (ASAEL), appears in a separate column and is identified with **bold** and *italicized* text. This subset of Aes (the ASAEL) contains events that are considered ‘expected’ for expedited reporting purposes only. Refer to the “CTEP, NCI Guidelines: Adverse Event Reporting Requirements” (<http://ctep.cancer.gov/>) for further clarification. The CAEPR may not provide frequency data; if not, refer to the Investigator’s Brochure for this information.

CAEPR for cediranib

**Comprehensive Adverse Events and Potential Risks list (CAEPR)
 for
 Cediranib (AZD2171, NSC 732208)**

The Comprehensive Adverse Events and Potential Risks list (CAEPR) provides a single list of reported and/or potential adverse events (AE) associated with an agent using a uniform presentation of events by body system. In addition to the comprehensive list, a subset, the Specific Protocol Exceptions to Expedited Reporting (SPEER), appears in a separate column and is identified with bold and italicized text. This subset of AEs (SPEER) is a list of events that are protocol specific exceptions to expedited reporting to NCI (except as noted below). Refer to the 'CTEP, NCI Guidelines: Adverse Event Reporting Requirements' http://ctep.cancer.gov/protocolDevelopment/electronic_applications/docs/aeguidelines.pdf for further clarification. Frequency is provided based on 1608 patients. Below is the CAEPR for Cediranib (AZD2171).

NOTE: Report AEs on the SPEER **ONLY IF** they exceed the grade noted in parentheses next to the AE in the SPEER. If this CAEPR is part of a combination protocol using multiple investigational agents and has an AE listed on different SPEERs, use the lower of the grades to determine if expedited reporting is required.

Version 2.15, November 7, 2018¹

Adverse Events with Possible Relationship to Cediranib (AZD2171) (CTCAE 5.0 Term) [n= 1608]			Specific Protocol Exceptions to Expedited Reporting (SPEER)
Likely (>20%)	Less Likely (<=20%)	Rare but Serious (<3%)	
BLOOD AND LYMPHATIC SYSTEM DISORDERS			
		Hemolytic uremic syndrome	
		Thrombotic thrombocytopenic purpura	
CARDIAC DISORDERS			
		Heart failure	
		Left ventricular systolic dysfunction	
ENDOCRINE DISORDERS			
	Hyperthyroidism		
	Hypothyroidism		Hypothyroidism (Gr 2)
GASTROINTESTINAL DISORDERS			
	Abdominal pain		Abdominal pain (Gr 3)
	Anal mucositis		Anal mucositis (Gr 2)
	Constipation		Constipation (Gr 3)
Diarrhea			Diarrhea (Gr 3)
	Dry mouth		Dry mouth (Gr 2)
	Dysphagia		Dysphagia (Gr 2)
		Gastrointestinal fistula ²	
		Gastrointestinal perforation ³	
	Mucositis oral		Mucositis oral (Gr 3)
Nausea			Nausea (Gr 3)
		Pancreatitis	
	Rectal mucositis		Rectal mucositis (Gr 2)
	Small intestinal mucositis		Small intestinal mucositis (Gr 2)
	Vomiting		Vomiting (Gr 3)

Adverse Events with Possible Relationship to Cediranib (AZD2171) (CTCAE 5.0 Term) [n= 1608]			Specific Protocol Exceptions to Expedited Reporting (SPEER)
Likely (>20%)	Less Likely (<=20%)	Rare but Serious (<3%)	
GENERAL DISORDERS AND ADMINISTRATION SITE CONDITIONS			
Fatigue			Fatigue (Gr 3)
HEPATOBIILIARY DISORDERS			
		Hepatic failure	
INFECTIONS AND INFESTATIONS			
	Infection ⁴		
INJURY, POISONING AND PROCEDURAL COMPLICATIONS			
		Wound complication	
INVESTIGATIONS			
	Alanine aminotransferase increased		Alanine aminotransferase increased (Gr 3)
	Alkaline phosphatase increased		
	Aspartate aminotransferase increased		Aspartate aminotransferase increased (Gr 3)
	Lymphocyte count decreased		
	Neutrophil count decreased		
	Platelet count decreased		
	Thyroid stimulating hormone increased		Thyroid stimulating hormone increased (Gr 2)
	Weight loss		Weight loss (Gr 2)
METABOLISM AND NUTRITION DISORDERS			
Anorexia			Anorexia (Gr 3)
	Dehydration		Dehydration (Gr 3)
	Hypophosphatemia		Hypophosphatemia (Gr 3)
MUSCULOSKELETAL AND CONNECTIVE TISSUE DISORDERS			
	Generalized muscle weakness		
NERVOUS SYSTEM DISORDERS			
	Dizziness		Dizziness (Gr 2)
	Headache		Headache (Gr 3)
	Lethargy		
		Leukoencephalopathy	
		Reversible posterior leukoencephalopathy syndrome	
RENAL AND URINARY DISORDERS			
		Nephrotic syndrome	
	Proteinuria		Proteinuria (Gr 2)
RESPIRATORY, THORACIC AND MEDIASTINAL DISORDERS			
	Cough		Cough (Gr 2)
	Dyspnea		Dyspnea (Gr 3)
	Laryngeal mucositis		Laryngeal mucositis (Gr 2)
	Pharyngeal mucositis		Pharyngeal mucositis (Gr 2)
	Tracheal mucositis		Tracheal mucositis (Gr 2)
Voice alteration			Voice alteration (Gr 2)
SKIN AND SUBCUTANEOUS TISSUE DISORDERS			
	Palmar-plantar erythrodysesthesia syndrome		Palmar-plantar erythrodysesthesia syndrome (Gr 2)

Adverse Events with Possible Relationship to Cediranib (AZD2171) (CTCAE 5.0 Term) [n= 1608]			Specific Protocol Exceptions to Expedited Reporting (SPEER)
Likely (>20%)	Less Likely (<=20%)	Rare but Serious (<3%)	
VASCULAR DISORDERS			
		Arterial thromboembolism	
Hypertension			Hypertension (Gr 3)
	Thromboembolic event		Thromboembolic event (Gr 4)
	Vascular disorders - Other (hemorrhage) ⁵		

¹This table will be updated as the toxicity profile of the agent is revised. Updates will be distributed to all Principal Investigators at the time of revision. The current version can be obtained by contacting [contact]. Your name, the name of the investigator, the protocol and the agent should be included in the e-mail.

²Gastrointestinal fistula includes Anal fistula, Colonic fistula, Duodenal fistula, Esophageal fistula, Enterovesical fistula, Gastric fistula, Gastrointestinal fistula, Ileal fistula, Jejunal fistula, Oral cavity fistula, Pancreatic fistula, Rectal fistula, and Salivary gland fistula under the GASTROINTESTINAL DISORDERS SOC.

³Gastrointestinal perforation includes Colonic perforation, Duodenal perforation, Esophageal perforation, Gastric perforation, Ileal perforation, Jejunal perforation, Rectal perforation, and Small intestinal perforation under the GASTROINTESTINAL DISORDERS SOC.

⁴Infections includes all 75 sites of infection under the INFECTIONS AND INFESTATIONS SOC.

⁵Hemorrhage is a known consequence of VEGF/VEGFR signaling inhibition. The majority of hemorrhage events reported were mild; however, serious events, defined as symptomatic bleeding in a critical area or organ system (e.g., eye, gastrointestinal tract, genitourinary [GU] tract, respiratory tract, and nervous system) have been reported.

Adverse events reported on cediranib (AZD2171) trials, but for which there is insufficient evidence to suggest that there was a reasonable possibility that cediranib (AZD2171) caused the adverse event:

BLOOD AND LYMPHATIC SYSTEM DISORDERS - Anemia; Blood and lymphatic system disorders - Other (polycythemia); Bone marrow hypocellular; Febrile neutropenia

CARDIAC DISORDERS - Atrial fibrillation; Atrial flutter; Cardiac arrest; Cardiac disorders - Other (premature ventricular complexes); Cardiac disorders - Other (valvular heart disease); Chest pain - cardiac; Mobitz (type) II atrioventricular block; Myocardial infarction; Palpitations; Pericardial effusion; Pericarditis; Restrictive cardiomyopathy; Sinus bradycardia; Sinus tachycardia; Supraventricular tachycardia

EAR AND LABYRINTH DISORDERS - Ear and labyrinth disorders - Other (ears feel full/plugged); Ear and labyrinth disorders - Other (viral labyrinthitis); Tinnitus; Vertigo

EYE DISORDERS - Blurred vision; Eye disorders - Other (blindness); Eye disorders - Other (visual disturbance); Papilledema; Photophobia; Retinal vascular disorder

GASTROINTESTINAL DISORDERS - Abdominal distension; Anal pain; Ascites; Bloating; Colitis; Colonic obstruction; Duodenal ulcer; Dyspepsia; Enterocolitis; Esophageal necrosis; Esophageal ulcer; Esophagitis; Flatulence; Gastric necrosis; Gastric ulcer; Gastroesophageal reflux disease; Gastrointestinal disorders - Other (diverticulitis); Gastrointestinal disorders - Other (hydrops); Gastrointestinal disorders - Other (tongue sensitivity); Ileus; Oral pain; Periodontal disease; Peritoneal necrosis; Rectal pain; Small intestinal obstruction

GENERAL DISORDERS AND ADMINISTRATION SITE CONDITIONS - Chills; Edema face; Edema limbs; Fever; Gait disturbance; Hypothermia; Malaise; Non-cardiac chest pain; Pain

HEPATOBIILIARY DISORDERS - Cholecystitis; Gallbladder obstruction; Hepatic pain; Hepatobiliary disorders - Other (bile duct obstruction); Hepatobiliary disorders - Other (jaundice cholestatic)

IMMUNE SYSTEM DISORDERS - Allergic reaction; Anaphylaxis; Immune system disorders - Other (systemic inflammatory response syndrome)

INJURY, POISONING AND PROCEDURAL COMPLICATIONS - Bruising; Dermatitis radiation; Fracture; Injury, poisoning and procedural complications - Other (tracheostomy malfunction); Intestinal stoma leak; Venous injury; Wound dehiscence

INVESTIGATIONS - Activated partial thromboplastin time prolonged; Blood bilirubin increased; Blood lactate dehydrogenase increased; CPK increased; Cardiac troponin I increased; Cardiac troponin T increased; Cholesterol high; Creatinine increased; Ejection fraction decreased; Electrocardiogram QT corrected interval prolonged; GGT increased; Hemoglobin increased; INR increased; Investigations - Other (elevated ammonia level); Investigations - Other (increased blood erythropoietin); Lipase increased; White blood cell decreased

METABOLISM AND NUTRITION DISORDERS - Acidosis; Hypercalcemia; Hyperglycemia; Hyperkalemia; Hypertriglyceridemia; Hypoalbuminemia; Hypocalcemia; Hypoglycemia; Hypokalemia; Hypomagnesemia; Hyponatremia; Metabolism and nutrition disorders - Other (failure to thrive)

MUSCULOSKELETAL AND CONNECTIVE TISSUE DISORDERS - Arthralgia; Avascular necrosis; Back pain; Bone pain; Chest wall pain; Muscle cramp; Muscle weakness lower limb; Muscle weakness upper limb; Myalgia; Myositis; Neck pain; Pain in extremity; Rotator cuff injury

NEOPLASMS BENIGN, MALIGNANT AND UNSPECIFIED (INCL CYSTS AND POLYPS) - Tumor pain

NERVOUS SYSTEM DISORDERS - Ataxia; Central nervous system necrosis; Cognitive disturbance; Depressed level of consciousness; Dysarthria; Dysgeusia; Dysphasia; Encephalopathy; Hydrocephalus; Ischemia cerebrovascular; Memory impairment; Muscle weakness left-sided; Nervous system disorders - Other (coma); Nervous system disorders - Other (right hemiparesis); Olfactory nerve disorder; Peripheral motor neuropathy; Peripheral sensory neuropathy; Seizure; Somnolence; Spinal cord compression; Stroke; Syncope; Transient ischemic attacks; Tremor

PSYCHIATRIC DISORDERS - Confusion; Delirium; Depression; Hallucinations; Insomnia; Suicide attempt

RENAL AND URINARY DISORDERS - Acute kidney injury; Chronic kidney disease; Cystitis noninfective; Hematuria; Urinary retention; Urinary tract obstruction

REPRODUCTIVE SYSTEM AND BREAST DISORDERS - Irregular menstruation; Menorrhagia; Vaginal fistula

RESPIRATORY, THORACIC AND MEDIASTINAL DISORDERS - Aspiration; Hypoxia; Pharyngolaryngeal pain; Pleural effusion; Pneumonitis; Pneumothorax; Pulmonary edema; Pulmonary fistula; Pulmonary hypertension; Sinus pain

SKIN AND SUBCUTANEOUS TISSUE DISORDERS - Alopecia; Dry skin; Hyperhidrosis; Nail loss; Pruritus; Purpura; Rash acneiform; Rash maculo-papular; Skin and subcutaneous tissue disorders - Other (petechiae); Skin and subcutaneous tissue disorders - Other (plantar warts); Skin ulceration; Urticaria

VASCULAR DISORDERS - Capillary leak syndrome; Flushing; Hypotension; Vasculitis

Note: Cediranib (AZD2171) in combination with other agents could cause an exacerbation of any adverse event currently known to be caused by the other agent, or the combination may result in events never previously associated with either agent.

CAEPR for olaparib

Comprehensive Adverse Events and Potential Risks list (CAEPR) for Olaparib (AZD2281, NSC 747856)

The Comprehensive Adverse Events and Potential Risks list (CAEPR) provides a single list of reported and/or potential adverse events (AE) associated with an agent using a uniform presentation of events by body system. In

addition to the comprehensive list, a subset, the Specific Protocol Exceptions to Expedited Reporting (SPEER), appears in a separate column and is identified with bold and italicized text. This subset of AEs (SPEER) is a list of events that are protocol specific exceptions to expedited reporting to NCI (except as noted below). Refer to the 'CTEP, NCI Guidelines: Adverse Event Reporting Requirements'

http://ctep.cancer.gov/protocolDevelopment/electronic_applications/docs/aeguidelines.pdf for further clarification. Frequency is provided based on 2073 patients. Below is the CAEPR for Olaparib (AZD2281).

NOTE: Report AEs on the SPEER **ONLY IF** they exceed the grade noted in parentheses next to the AE in the SPEER. If this CAEPR is part of a combination protocol using multiple investigational agents and has an AE listed on different SPEERs, use the lower of the grades to determine if expedited reporting is required.

Version 2.3, June 18, 2018¹

Adverse Events with Possible Relationship to Olaparib (AZD2281) (CTCAE 5.0 Term) [n= 2073]			Specific Protocol Exceptions to Expedited Reporting (SPEER)
Likely (>20%)	Less Likely (<=20%)	Rare but Serious (<3%)	
BLOOD AND LYMPHATIC SYSTEM DISORDERS			
Anemia			Anemia (Gr 4)
GASTROINTESTINAL DISORDERS			
	Abdominal distension		
	Abdominal pain		Abdominal pain (Gr 2)
	Constipation		Constipation (Gr 2)
Diarrhea			Diarrhea (Gr 2)
	Dyspepsia		Dyspepsia (Gr 2)
Nausea			Nausea (Gr 3)
Vomiting			Vomiting (Gr 3)
GENERAL DISORDERS AND ADMINISTRATION SITE CONDITIONS			
	Edema limbs		
Fatigue			Fatigue (Gr 3)
	Fever		
INFECTIONS AND INFESTATIONS			
	Infection ²		
INVESTIGATIONS			
	Creatinine increased		
	Lymphocyte count decreased		
	Neutrophil count decreased		
METABOLISM AND NUTRITION DISORDERS			
Anorexia			Anorexia (Gr 2)
MUSCULOSKELETAL AND CONNECTIVE TISSUE DISORDERS			
	Arthralgia		
	Back pain		
NEOPLASMS BENIGN, MALIGNANT AND UNSPECIFIED (INCL CYSTS AND POLYPS)			
		Leukemia secondary to oncology chemotherapy	
		Myelodysplastic syndrome	
NERVOUS SYSTEM DISORDERS			
	Dizziness		Dizziness (Gr 2)
	Dysgeusia		Dysgeusia (Gr 2)
	Headache		Headache (Gr 2)
RESPIRATORY, THORACIC AND MEDIASTINAL DISORDERS			

Adverse Events with Possible Relationship to Olaparib (AZD2281) (CTCAE 5.0 Term) [n= 2073]			Specific Protocol Exceptions to Expedited Reporting (SPEER)
Likely (>20%)	Less Likely (<=20%)	Rare but Serious (<3%)	
	Cough		Cough (Gr 2)
	Dyspnea		Dyspnea (Gr 2)
		Pneumonitis	

¹This table will be updated as the toxicity profile of the agent is revised. Updates will be distributed to all Principal Investigators at the time of revision. The current version can be obtained by contacting [contact]. Your name, the name of the investigator, the protocol and the agent should be included in the e-mail.

²Infection may include any of the 75 infection sites under the INFECTIONS AND INFESTATION SOC.

Adverse events reported on olaparib (AZD2281) trials, but for which there is insufficient evidence to suggest that there was a reasonable possibility that olaparib (AZD2281) caused the adverse event:

CARDIAC DISORDERS - Cardiac disorders - Other (nodal rhythm); Chest pain - cardiac; Sinus tachycardia
EAR AND LABYRINTH DISORDERS - Tinnitus
ENDOCRINE DISORDERS - Hypothyroidism
GASTROINTESTINAL DISORDERS - Ascites; Colitis; Colonic obstruction; Dry mouth; Dysphagia; Flatulence; Gastroesophageal reflux disease; Gastrointestinal disorders - Other (gastrointestinal hemorrhage); Gastrointestinal disorders - Other (intestinal obstruction); Gastrointestinal disorders - Other (intestinal perforation); Ileus; Jejunal perforation; Mucositis oral; Pancreatitis; Periodontal disease; Rectal hemorrhage; Small intestinal obstruction; Stomach pain
GENERAL DISORDERS AND ADMINISTRATION SITE CONDITIONS - Malaise; Non-cardiac chest pain
IMMUNE SYSTEM DISORDERS - Immune system disorders - Other (systemic inflammatory response syndrome)
INJURY, POISONING AND PROCEDURAL COMPLICATIONS - Fracture; Gastrointestinal anastomotic leak; Injury, poisoning and procedural complications - Other (vena cava injury); Wound dehiscence
INVESTIGATIONS - Alanine aminotransferase increased; Aspartate aminotransferase increased; Blood bilirubin increased; GGT increased; Hemoglobin increased; Lipase increased; Platelet count decreased; Serum amylase increased; Weight loss; White blood cell decreased
METABOLISM AND NUTRITION DISORDERS - Dehydration; Hyperglycemia; Hypermagnesemia; Hypocalcemia; Hypokalemia; Hypomagnesemia; Hyponatremia
MUSCULOSKELETAL AND CONNECTIVE TISSUE DISORDERS - Avascular necrosis; Bone pain; Generalized muscle weakness; Muscle cramp; Muscle weakness lower limb; Myalgia; Neck pain; Pain in extremity; Rotator cuff injury
NEOPLASMS BENIGN, MALIGNANT AND UNSPECIFIED (INCL CYSTS AND POLYPS) - Tumor pain
NERVOUS SYSTEM DISORDERS - Amnesia; Ataxia; Cognitive disturbance; Concentration impairment; Encephalopathy; Intracranial hemorrhage; Peripheral sensory neuropathy; Stroke; Syncope; Transient ischemic attacks
PSYCHIATRIC DISORDERS - Anxiety; Confusion; Delirium; Hallucinations; Insomnia
RENAL AND URINARY DISORDERS - Acute kidney injury; Renal and urinary disorders - Other (decreased glomerular filtration rate); Renal and urinary disorders - Other (hydronephrosis); Urinary tract obstruction
REPRODUCTIVE SYSTEM AND BREAST DISORDERS - Vaginal hemorrhage
RESPIRATORY, THORACIC AND MEDIASTINAL DISORDERS - Bronchopulmonary hemorrhage; Oropharyngeal pain; Pleural effusion; Respiratory failure; Respiratory, thoracic and mediastinal disorders - Other (chronic obstructive pulmonary disease)

SKIN AND SUBCUTANEOUS TISSUE DISORDERS - Alopecia; Pruritus; Rash maculo-papular
VASCULAR DISORDERS - Flushing; Hot flashes; Hypertension; Hypotension; Thromboembolic event

Note: Olaparib (AZD2281) in combination with other agents could cause an exacerbation of any adverse event currently known to be caused by the other agent, or the combination may result in events never previously associated with either agent.

